4.3.1.3.6 Assessment of Causality

The Investigator will assess the *causal relationship* between each unsolicited systemic AE and the investigational product administered as either **Not related** or **Related**, based on the following definitions:

- Not related – The AE is clearly / most probably caused by other etiologies such as an underlying condition, therapeutic intervention, or concomitant therapy; or the delay between vaccination and the onset of the AE is incompatible with a causal relationship; or the AE started before the first vaccination (screening phase, if applicable)
- Related – There is a “reasonable possibility” that the AE was caused by the product administered, meaning that there is evidence or arguments to suggest a causal relationship

Note: By convention, all AEs reported at the injection site (whether solicited or unsolicited) and all solicited systemic AEs are considered to be related to the administered product and therefore are referred to as reactions and do not require the Investigator’s opinion on relatedness.

AEs likely to be related to the product, whether serious or not, that persist at the end of the study will be followed up by the Investigator until their complete disappearance or the stabilization of the subject’s condition. The Investigator will inform the Sponsor of the date of final disappearance of the event or the date of “chronicity” establishment.

4.4 Derived Endpoints: Calculation Methods

4.4.1 Safety

4.4.2 Solicited Reactions

4.4.2.1 Daily Intensity

All daily records for solicited reactions will be derived into daily intensity according to the following classification: None, Grade 1, Grade 2, Grade 3, or Missing (Unknown).

For the derivation of daily intensities the following sequential steps will be applied:

- 1) Solicited reactions (except Fever/Pyrexia) with an investigator presence recorded as “No” and with all daily records missing (unknown), then all daily intensities will be derived as None.
- 2) For non-measurable (NM) solicited reactions, the daily intensities will correspond to the daily records reported in the clinical database. For measurable solicited reactions, the daily measurements reported in the clinical database will be converted based upon the intensity scales defined in the protocol; this assumes a reaction that is too large to measure (NM) is Grade 3.

Note: The maximum intensity on the ongoing period is derived from the record of the maximum intensity/measurement after the end of the solicited period following the rule described above.

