^a The term “life-threatening” refers to an event in which the subject was at risk of death at the time of the event; it does not refer to an event which hypothetically might have caused death if it were more severe.

^b All medical events leading to hospitalizations will be recorded and reported as SAEs, with the exception of: hospitalization planned before inclusion into the study or outpatient treatment with no hospitalization.

^c “Persistent or significant disability or incapacity” means that there is a substantial disruption of a person’s ability to carry out normal life functions.

Medical and scientific judgment should be exercised in deciding whether expedited reporting is appropriate in other situations, such as IMEs that may not be immediately life-threatening or result in death or hospitalization but may jeopardize the health of the subject or may require intervention to prevent one of the other outcomes listed in the definition above. These IMEs should also usually be considered serious. Examples of such events include allergic bronchospasm requiring intensive treatment in an emergency room or at home, blood dyscrasias or convulsions that do not result in inpatient hospitalization, or the development of drug dependency or drug abuse, new-onset diabetes, or autoimmune disease.

Adverse Reaction:

All noxious and unintended responses to a medicinal product related to any dose should be considered adverse reactions (AR).

(The phrase “responses to a medicinal product” means that a causal relationship between a medicinal product and an AE is at least a reasonable possibility)

The following additional definitions are used by Sanofi Pasteur:

Immediate Event/Reaction:

Immediate events are recorded to capture medically relevant unsolicited systemic AEs (including those related to the product administered) that occur within the first 30 minutes after vaccination.

Solicited Reaction:

A solicited reaction is an “expected” adverse reaction (sign or symptom) observed and reported under the conditions (nature and onset) prelisted in the protocol and CRB (e.g., injection site tenderness or irritability occurring between D0 and D07 after vaccination).

By definition, solicited reactions are to be considered as being related to the product administered.

For injectable vaccines, solicited reactions can either be solicited injection site reactions or solicited systemic reactions.

The assessment of these reactions by the investigator is mandatory.

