4.4.2.1.2 Presence

Presence is derived from the maximum overall intensity on the period considered:

- None: No presence
- Grade 1, Grade 2, or Grade 3: Presence
- Missing or Unknown: Missing presence

Subjects with at least one non-missing presence for a specific endpoint will be included in the analysis. Conversely, those without a non-missing presence will not be included in the analysis of the endpoint.

The time period is displayed as D0-D3, D4-D7, D8 and later.

Note: solicited reactions with Missing presence will not be included in the safety analysis tables.

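### For solicited reactions other than fever, an investigator's No without daily records counts as no reaction, while a Yes without daily records drops out of the rate

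*SAP*

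**What the plan says.** SAP 4.4.2.1 derives daily intensities in sequential steps. Step 1 applies where the investigator answered No, for every solicited reaction but fever. Its condition and consequence read: "and with all daily records missing (unknown), then all daily intensities will be derived as None".

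Step 2 covers the rest. For non-measurable reactions "the daily intensities will correspond to the daily records reported in the clinical database". For measurable reactions the recorded measurements are converted with the intensity scale, and a reaction too large to measure is taken as Grade 3. Neither step refers to an investigator answer of Yes.

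SAP 4.4.2.1.2 derives presence from maximum intensity alone. None gives no presence, and Grades 1 to 3 give presence. The remaining category reads "Missing or Unknown: Missing presence". On the denominator the section says that "those without a non-missing presence will not be included in the analysis of the endpoint", and it closes with "Note: solicited reactions with Missing presence will not be included in the safety analysis tables".

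Protocol 9.3.2.1 says of solicited reactions: "The assessment of these reactions by the investigator is mandatory". An investigator's view is therefore expected for these reactions.

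**The concern.** The same source is accepted when it reports no reaction and ignored when it reports one. A child with an investigator No and no daily records stays in the denominator as a non-event. A child with an investigator Yes and no daily records disappears. Where both kinds of child exist, the plan keeps the non-reactors and omits reactions that the investigator confirmed.

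Describing the safety profile is the purpose of both observational objectives (SAP 2.3), and solicited reaction rates are core outputs for it. No hypothesis test depends on them (SAP 5.1.3), so what is at stake is the accuracy of descriptive rates.

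The SAP is more inclusive elsewhere. Under 4.4.2.2.1 an unsolicited event counts if it has a verbatim term and is not Grade 0, so an unknown grade does not remove it. In the discontinuation table by system organ class and preferred term (4.4.2.5.5), unsolicited events qualify with a missing grade, whereas solicited events need at least Grade 1.

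**Working it through.** The plan states no figure on this point, so there is nothing to reproduce. The check is algebraic, followed by an illustration.

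**Scope.** SAP Tables 4.2 and 4.3 list 3 injection-site and 6 systemic solicited reactions. Fever is exempt from step 1, so 3 + 6 − 1 = 8 reactions are affected. For fever neither answer is used, and a child with no temperature record is left out either way.

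**Notation, per reaction.**
- R: daily records show a reaction.
- N: daily records show none.
- Y: all daily records missing, investigator Yes.
- M: all daily records missing, investigator No.

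**Rates.**
- As planned: R/(R+N+M).
- Both answers used: (R+Y)/(R+Y+N+M).
- Shortfall (second minus first): Y(N+M)/[(R+N+M)(R+Y+N+M)].

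The shortfall is never negative. It is positive whenever Y > 0 and at least one child counts as a non-reactor. It is exactly zero when Y = 0.

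**Size.** The documents give neither the share m of children lacking all daily records nor the true rate p. Both are assumed here. If children without records react at the same rate as the others, the planned rate is p(1−m)/[(1−m)+m(1−p)] = p(1−m)/(1−mp), and the shortfall is mp(1−p)/(1−mp).

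| p | m | Planned rate | Shortfall (points) |
|---|---|---|---|
| 5% | 1% | 4.95% | 0.05 |
| 5% | 10% | 4.52% | 0.48 |
| 20% | 1% | 19.84% | 0.16 |
| 20% | 10% | 18.37% | 1.63 |
| 50% | 1% | 49.75% | 0.25 |
| 50% | 10% | 47.37% | 2.63 |

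For example, with p = 50% and m = 10%: 0.45/0.95 = 47.37%, and 50 − 47.37 = 2.63.

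**In whole children.** Take 435 per group, the planned enrollment of Groups 1 and 2 (SAP 5.5), with R = 196, N = 195, Y = 22, M = 22. The planned rate is 196/413 = 47.5% (exact 95% CI 42.6 to 52.4). With both answers used it is 218/435 = 50.1% (45.3 to 54.9). The formula gives 22 × 217/(413 × 435) = 2.7 points.

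**If the equal-rate assumption fails.** Suppose m = 10% and half of the children without records are Yes.
- p = 5% among the others: planned 0.045/0.95 = 4.74%; both used 0.045 + 0.05 = 9.50%; shortfall 4.8 points.
- p = 20% among the others: planned 0.18/0.95 = 18.95%; both used 0.18 + 0.05 = 23.0%; shortfall 4.1 points.

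**The case against.** The strongest reply is that such Yes cases may be few or absent. Step 2 works from records in the clinical database, not from the paper diary, and several procedures fill that database when the diary is deficient. Protocol 13.2 has the coordinator obtain verbal clarification and transfer it to the case report book. Protocol 11.1 has the site interview parents and try to clarify anything incomplete. Protocol 11.2 provides consistency checks and queries. These should make wholly missing records rarer. They do not say what happens to a Yes that still has none, so the gap in the rule stands.

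A second reply is that measurements should outrank flags. SAP 4.4.2.1.6 sets aside the investigator's ongoing flag on that ground. This has force where a measurement exists, but here there is none, and step 1 already relies on the flag for No. Nor does the no-replacement rule in Protocol 12.3.1 defend the plan, because step 1 is itself a replacement.

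A third reply is scale. The exact interval at 435 children is about 5 points either side of the estimate, wider than the shortfalls at equal reaction rates. The analysis is descriptive and the rule is the same in every group. That limits the consequence but does not justify a one-directional rule.

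A reader might go further in three ways that the documents do not support:
- **That a child with some days None and the rest missing is misclassified when the investigator said Yes.** SAP 4.4.2.1.1 takes the maximum of the daily intensities and does not say how None and Missing combine. Overriding days recorded as None would also set a flag above actual records.
- **That No should be treated as missing too.** The case report form is not in the documents. If sites leave daily fields blank after a No, this would remove true non-reactors. With an assumed true rate of 40% and half of the No children lacking daily entries, the reported rate becomes 0.40/(0.40 + 0.30) = 57%.
- **That the group comparison is distorted.** This needs the cases to differ between groups, and nothing in the documents shows that they do.

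**Conclusion.** The asymmetry is in the text. For eight of the nine solicited reactions, following the SAP exactly keeps No children without daily records and omits Yes children without daily records. Any resulting error against using both answers is downward.

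The size is conditional. It is about 0.05 to 2.6 points for true rates of 5% to 50%, if 1% to 10% of children lack all daily records and react as often as the others. It is larger if a higher share of them are Yes, and zero if there is no such Yes. All of these shares are assumptions.

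A reader might infer that the reported rates are in fact biased downward. The documents do not support that. They give no count of Yes cases without daily records, and if there are none and the No answers are correct, the planned rate is right.

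**What to change.** In SAP 4.4.2.1 and 4.4.2.1.2, add a rule for the same eight reactions: when investigator presence is Yes and all daily records are missing, derive presence as Yes with intensity Missing. Count the child in the numerator and denominator of the any-reaction row, add a grade-missing row, and report the number of such cases per group. Leave step 1 as it is for No, and do not override any day recorded as None.

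The cost is a short addition to the SAP and its derivation code, on a field already in the database, plus one table row. Reported rates may rise slightly, and these events will have no grade, onset day or duration. If the count proves to be zero in every group, the tables do not change and the report can say so.

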4.4.2.1.1 Maximum Intensity

Maximum overall intensity is derived from the daily intensities as described in [Section 4.4.2.1](#) and is calculated as the maximum of the daily intensities over the period considered.

4.4.2.1.2 Presence

Presence is derived from the maximum overall intensity on the period considered:

- None: No presence
- Grade 1, Grade 2, or Grade 3: Presence
- Missing or Unknown: Missing presence

Subjects with at least one non-missing presence for a specific endpoint will be included in the analysis. Conversely, those without a non-missing presence will not be included in the analysis of the endpoint.

The time period is displayed as D0-D3, D4-D7, D8 and later.

Note: solicited reactions with Missing presence will not be included in the safety analysis tables.

4.4.2.1.3 Time of Onset

Time of onset is derived from the daily intensities computed as described in [Section 4.4.2.1](#). It corresponds to the first day with intensity of Grade 1, Grade 2, or Grade 3.

Note: If a reaction is not continuous (i.e., reaction occurs over two separate periods of time intervened by at least one daily intensity Missing or None) then the time of onset is the first day of the first occurrence.

Time of onset is presented as D0-D3, D4-D7.

4.4.2.1.4 Number of Days of Occurrence During the Solicited Period

Number of days of occurrence over the solicited period (D0 to D7) considered is derived from the daily intensities computed as described in [Section 4.4.2.1](#). It corresponds to the number of days with daily intensities of Grade 1, Grade 2, or Grade 3. Number of days of occurrence on the solicited period with a specified intensity (e.g, Grade 3) may also be derived.

4.4.2.1.5 Overall Number of Days of Occurrence

If a reaction is ongoing at the end of the solicited period, then the overall number of days of occurrence after each vaccination is derived from the daily intensities and the stop date of the reaction after the end of the solicited period. The overall number of days of occurrence is:

(The stop date of the solicited event – last vaccination date) + (number of days of occurrence within the solicited period) – length of the solicited period + 1

If the stop date of the solicited reaction is missing or incomplete (contains MD), the overall number of days of occurrence will be considered as Missing.

4.4.2.1.6 Ongoing

Ongoing is derived from the last daily intensity of the solicited period computed as described in [Section 4.4.2.1](#) and the maximum intensity on the ongoing period. The investigator's ongoing flag is not used because the measurement would determine the ongoing status of the reaction.

- Ongoing: if the last daily intensity of the solicited period is at least Grade 1 and the maximum intensity on the ongoing period is at least Grade 1
- Not ongoing: if the last daily intensity of the solicited period is None or the maximum intensity on the ongoing period is None.
- Missing: all other conditions (in this case, it is not included in the denominator of the ongoing analysis in the safety tables)

4.4.2.2 Unsolicited AEs

4.4.2.2.1 Presence

An observation will be considered an event if it has at least a verbatim term and is not Grade 0 (None) intensity event.

Note: Unsolicited AEs with Grade 0 (None) intensity for a specific endpoint will not be included in the safety analysis tables.

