4.3.1.3.3 Unsolicited Adverse Events

In addition to recording solicited reactions, parents / guardians will be instructed to record any other medical events that may occur during the 30-day period after each vaccination. Space will be provided in the diary card for this purpose.

Information on SAEs will be collected and assessed throughout the study, from Visit 1 until 6 months after the last vaccination. Any SAE occurring at any time during the study will be reported by the Investigator in the CRB according to the completion instructions provided by the Sponsor; this includes checking the “Serious” box on the AE CRF and completing the appropriate Safety Complementary Information CRF. All information concerning the SAE is to be reported either as part of the initial reporting or during follow-up reporting if relevant information became available later (e.g., outcome, medical history, results of investigations, copy of hospitalization reports. In case a subject experiences febrile convulsion (neurological event associating fever and seizure), the assessment will be performed according to the “Guideline for definition and collection of cases of febrile convolution”, and this event will be considered an SAE.

For each unsolicited AE (whether serious or non-serious), the following information is to be recorded:

- Start and stop dates
- Intensity of the event:

For measurable unsolicited AEs that are part of the list of solicited reactions, the size of the AE as well as the temperature for fever will be collected and analyzed based on the corresponding scale used for solicited reactions.

All other unsolicited AEs will be classified according to the following intensity scale:

- Grade 1: A type of AE that is usually transient and may require only minimal treatment or therapeutic intervention. The event does not generally interfere with usual activities of daily living.
- Grade 2: A type of AE that is usually alleviated with additional therapeutic intervention. The event interferes with usual activities of daily living, causing discomfort but poses no significant or permanent risk of harm to the research participant.
- Grade 3: A type of AE that interrupts usual activities of daily living, or significantly affects clinical status, or may require intensive therapeutic intervention.

- Whether the AE was related to the investigational product (for unsolicited systemic AEs)

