4.4.2.2.2 Intensity

Intensity for unsolicited AE will be derived according to the following classification:

Grade 0 (None), Grade 1, Grade 2, Grade 3, or Unknown (or missing).

If the unsolicited AE is measurable and its preferred term is part of the list of solicited reactions, then the measurement is derived based upon and following the same rule than the intensity scales defined in the protocol for that measurable injection site or systemic reaction.

Intensity for the other unsolicited AEs will correspond to the value reported in the CRF.

The maximum intensity corresponds to the highest intensity for a unique term.

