4.4.2.2.4 Time of Onset

Time of onset is derived from the start date of the unsolicited AE and the date of last vaccination as described in [Section 4.4.2.2.3](#):

Time of Onset = start date of the unsolicited AE - date of last vaccination before the unsolicited AE (if D0 is the first vaccination day).

The time of onset is considered as missing only if one or both dates are missing or partially missing.

The unsolicited AEs will be analyzed “Within 30 days” after each vaccination, which corresponds to AEs with a time of onset between day 0 and day 30.

Unsolicited AE that occurred before vaccination (negative time of onset) will not be included in analysis but will be listed separately.

Unsolicited AE which is non-serious, non-AESI and non-MAAE that occurred with a time of onset higher than defined above will not be included in analysis but will be listed separately.

- For unsolicited AE with missing day, month and year, the unsolicited AE will be classified as “Within 30 days”
- For unsolicited AE with partially missing start date, the partial available information will be used to determine if this AE is classified “Within 30 days” or “Not within 30 days”. An AE will be categorized as “Not within 30 days” only if there is clear evidence from the

partially missing start date that this AE happens before the first vaccination or after the last vaccination + 30 days. In all other situations, this AE is considered as “Within 30 days”. Situations may happen as:

- If the start date of AE has missing Day and non-missing Month and Year
 - If the “Month/Year of AE start date” < “Month/Year of first vaccination date”, then it is clear that this unsolicited AE happened before the first vaccination and this unsolicited AE will not be included in the analysis but will be listed separately.
 - Else if the “Month/Year of last vaccination date” <= “Month/Year of AE start date” <= “Month/Year of (last vaccination date + 30 days)”, then this unsolicited AE will be categorized as “Within 30 days”.
 - Else if the “Month/Year of AE start date” > “Month/Year of (last vaccination date + 30 days)”, then this unsolicited AE will be categorized as “not within 30 days”. If the AE is non-serious, non-AESI and non-MAAE, then it will not be included in the analysis but will be listed separately.
- If the start date of AE has missing Day and Month and non-missing Year:

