4.4.2.4 Medically-Attended Adverse Event (MAAE)

An event will be considered as an MAAE if “Yes” is checked for “Is the event an MAAE?” in the CRF.

MAAEs will be analyzed throughout the study using the following periods:

- During the entire study period after any dose from D0 to last phone call (i.e., all MAAEs that occurred during the study)
- From Day 0 to Day 30 after each vaccination

A MAAE with missing time of onset will be considered to have occurred just after the vaccination indicated by the visit number, so will be included in the safety analysis tables mentioned above.

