5.3.1.3 Intensity

For unsolicited AEs, missing intensities will remain missing and will not be imputed.

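### The SAP's Grade 0 exclusion has no exemption for serious or medically attended events, so a late-onset fever with a recorded temperature below 38.0°C can drop out of the SAE and MAAE tables

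*SAP*

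**What the plan says.** SAP 4.4.2.2.1 (Presence) defines what counts as an unsolicited AE: "An observation will be considered an event if it has at least a verbatim term and is not Grade 0 (None) intensity event". A note adds the consequence: "Unsolicited AEs with Grade 0 (None) intensity for a specific endpoint will not be included in the safety analysis tables". The section mentions no exception for serious events, AESIs or MAAEs, and no listing of what is removed.

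SAP 4.4.2.2.2 (Intensity) allows five categories: Grades 0 to 3, and unknown or missing. The grade is derived from the measurement under this condition: "If the unsolicited AE is measurable and its preferred term is part of the list of solicited reactions". Other unsolicited AEs keep the intensity entered on the CRF. SAP 4.3.1.3.3 says the same for fever in particular: "the temperature for fever will be collected and analyzed based on the corresponding scale used for solicited reactions".

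SAP Table 4.3 lists fever (preferred term pyrexia) as a solicited reaction. Grade 1 begins at 38.0°C (100.4°F), and no band is printed below it.

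SAP 5.3.1.3 covers absent grades: "For unsolicited AEs, missing intensities will remain missing and will not be imputed".

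SAP 4.4.2.3 and 4.4.2.4 classify SAEs and MAAEs by a CRF tick box. Each has a whole-study period; for MAAEs it reads "all MAAEs that occurred during the study".

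**The concern.** Whether an event is serious depends on outcome or action taken, and whether it is an MAAE depends on unplanned care being sought. Neither depends on a thermometer reading. In Protocol 9.3.2.2 the SAE endpoint does not list intensity at all, and the MAAE endpoint lists it only as one descriptor. A filter on derived grade that comes before the SAE and MAAE flags can therefore leave those tables incomplete against their own endpoints.

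The filter also works the wrong way round on documentation. A medically attended fever with no temperature on file stays in; the same fever with a documented value below 38.0°C can be removed.

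The SAP's authors handled this elsewhere. The late-onset exclusion in 4.4.2.2.4 is confined to unflagged events, which are then listed: "Unsolicited AE which is non-serious, non-AESI and non-MAAE that occurred with a time of onset higher than defined above will not be included". The Grade 0 exclusion has neither protection. Describing safety is a stated objective of the study, so complete SAE and MAAE tables matter.

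**Working it through.** The plan gives no figure on this point, so the check is a trace through the rules.

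1. **Which events are reached.** Fever starting between Day 0 and Day 7 is a solicited reaction and follows other derivation rules. Fever starting on Day 8 or later is unsolicited (SAP 4.3.1.1). Unsolicited AEs include SAEs (same section), and MAAEs are recorded as unsolicited AEs up to Day 30 (SAP 4.3.1.3.5). SAP 4.4.2.2.4 also treats MAAEs with later onset as unsolicited AEs, because it has to exempt them.
2. **How they are graded.** Pyrexia is measurable and on the solicited list, so 4.4.2.2.2 takes the grade from the temperature. The threshold agrees in both units: 38.0 × 9/5 + 32 = 100.4°F.
3. **Where a value below 38.0°C falls.** It is not missing and fits none of Grades 1 to 3. Of the five categories, Grade 0 is the one that remains.
4. **What Grade 0 does.** Under 4.4.2.2.1 the observation is not an event and is left out of the tables.
5. **Whether the flags rescue it.** The rules in 4.4.2.3 and 4.4.2.4 are worded as applying to an event. They contain no explicit override of 4.4.2.2.1.
6. **Discontinuation.** For the table by system organ class and preferred term, 4.4.2.5.5 counts an unsolicited AE only if it is Grade 1 or higher, or missing. Grade 0 is not counted.

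| Unsolicited AE flagged serious or MAAE | Derived intensity | Tabulated under 4.4.2.2.1? |
|---|---|---|
| Pyrexia, 37.9°C recorded | Grade 0 (by inference) | No |
| Pyrexia, 38.0°C recorded | Grade 1 | Yes |
| Pyrexia, no temperature recorded | Unknown or missing | Yes |
| Event under another preferred term, such as a febrile seizure | As entered on the CRF | Unaffected by the temperature |

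Rows 1 and 3 differ only in whether a reading was written down.

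**The case against.** Four arguments on the other side carry weight.

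- **The key step is an inference.** Nothing states that a reading below 38.0°C is Grade 0, and an off-scale value could conceivably be classed as unknown. This stands as a limit on certainty, although Grade 0 is the more natural reading.
- **The SAE and MAAE sections can be read as self-standing.** They sit beside 4.4.2.2 and classify by flag, and their whole-study periods speak of all such events. A programmer following them alone would keep every flagged event. This also stands, so the exact finding is that the sections conflict and need reconciling. A reader might infer that the SAP definitely deletes every such fever from every safety table; the text does not settle that.
- **The reach is narrow.** Parents are told to measure at any apparent fever, and the site records the highest value. Queries and data review before lock may catch a pyrexia below the documents' own fever threshold. For unflagged events the filter simply applies that definition, which is reasonable.
- **Other safeguards exist.** SAEs go to the sponsor within 24 hours and are reconciled between databases whatever their grade (Protocol 10.1 and 11.2). A participant with an adverse event marked as final status on the completion form still appears in the disposition and safety overview tables (SAP 4.4.2.5.5). The safety analysis is descriptive, and the rule is the same in every group.

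These arguments limit the consequences. They do not supply the missing exemption or listing, and safety reporting outside the analysis does not make a study table complete.

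**Conclusion.** The point holds as a gap in the SAP that should be closed. As written, 4.4.2.2.1 can remove flagged SAEs and MAAEs that 4.4.2.3, 4.4.2.4 and Protocol 9.3.2.2 would count. The conclusion assumes that a recorded temperature below 38.0°C is classed as Grade 0, and that the presence rule is applied before the SAE and MAAE flags.

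The size cannot be derived: the documents give no rate of medically attended fever and no distribution of recorded temperatures. The number is probably small. A reader might be tempted to estimate affected children per group, but any such figure would rest on rates without a source in the documents.

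Two wider readings also fail. Injection site redness and swelling are not caught in the same way, because their Grade 1 starts at any size above 0 mm. The AESIs are not exposed either, because none of the four is a solicited term. In practice the gap concerns pyrexia with onset on Day 8 or later. For a discontinued participant, what can be lost is the event-level row, not the participant's place in the disposition and overview tables when the completion form records an adverse event.

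**What to change.** - In SAP 4.4.2.2.1, limit the Grade 0 exclusion to unsolicited AEs that are non-serious, non-MAAE and did not cause study discontinuation. A non-AESI condition may be added to match 4.4.2.2.4, although it changes nothing in practice.
- Tabulate flagged events with intensity shown as below Grade 1, and list them.
- Align the grade condition in 4.4.2.5.5, so that a discontinuation event below Grade 1 appears in the table by system organ class and preferred term.
- State in 4.4.2.2.2 how a recorded temperature below 38.0°C is classed.

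The cost is small: essentially one sentence and one filter condition, plus the matching edits in the two other sections. The downside is a slightly higher count of fever SAEs and MAAEs. The exclusion of unflagged readings below 38.0°C stays as it is.
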